Trial: **Virtual Patient Behavioral Response Training for Family Caregivers**

ClinicalTrials.gov ID: **NCT04489303**

Date: **05/13/2022 (updated)**

Investigator: **[name]**

Research Site:

Photozig, Inc.
[name]
[name]
[name]

Project Summary

The main cause of behavioral symptoms in patients with Alzheimer's disease (AD) is the deterioration of brain cells which causes a decline in the individual's ability to make sense of the world. Coping with such difficult behaviors is challenging for many caregivers, and it is associated with many distressful situations.

The stress of dementia caregiving is influenced by several factors, such as severity of dementia symptoms, how challenging distressful situations are perceived by caregivers, and available resources. Although information and programs about dementia are available to the public, an essential missing tool is how to deal with difficult behaviors of dementia patients in an effective manner, as they are very common and demanding.

The goal of this project is to develop the Virtual Patient Behavioral Response (VPBR) training to improve skills on how to respond to dementia behavioral problems and enhance caregiver coping. We will implement this training in a mobile app (Caring Response App, CRA). The expected benefits include improved psychological health in caregivers and reduced stress related to behavioral disturbances of AD patients.

Protocol

Overview:

1. Recruit subjects: caregivers of individuals with Alzheimer's Disease or other dementia will be recruited.
2. Randomize subjects: participants will be assigned to the study group or the control group.
3. Collect pre-data: Before intervention, we will collect pre-data to establish the baseline status of participants.
4. Deploy treatments: For both study and control groups, we will send instructions and materials.
5. Collect post-data: We will collect post-treatment data after 3 months.

Research Participants: 150 dementia family caregivers (planned enrollment) will be recruited:

Inclusion Criteria:

- Care for an individual with Alzheimer's Disease or other dementia.
- Own a smartphone or tablet and have Internet access.
- Minimum age of 18 years old.
- Spend at least 8 hours/week caring for a person with dementia.

Exclusion Criteria:

- Severe psychological or physical illness.
- Inability to read and follow English instructions.
- High level of depressive symptoms.
- Unwillingness to participate in all aspects of the study.

Informed consent will be obtained, and participants will receive a stipend for their participation.

Methods: The effectiveness investigation of the Caring Response App (CRA) will be implemented with a pre-post randomized trial of 3 months. As it takes 3 months to complete the entire program, post testing will happen about 3 months after pre-testing. The trial will have two levels: the CRA treatment package; and a control condition comprised of existing educational programs, information for caregivers, and other resources. Outcome measures of both groups will be recorded at baseline and after 3 months.

- CRA Condition (75 subjects): Participants will receive the Caring Response mobile app containing the coping skills training.
- Control Condition (75 subjects): Participants will receive a traditional educational/resources program, containing a workbook and online resources.

Procedures: Participants will receive and complete informed consent. After initial assessment, subjects will be randomized to either CRA or the control condition, instructions will be distributed. After 3 months, all subjects will be interviewed for the post-intervention assessment.

Statistical Analysis Plan

Main study hypothesis: "CRA will contribute to lower burden of care (RMBPC), alleviate depression (measured by CES-D), and decrease stress (measured by PSS)."

Main Outcome Measures:

- Burden of care: level of bother or stress due to disruptive behaviors: we will apply the Revised Memory and Behavior Problems Checklist (RMBPC), with 24 items describing possible troublesome behaviors of care receiver and effect (bother and stress) on caregiver.
- Depression: level of Depressive Symptoms: their presence and strength will be assessed using the Center for Epidemiological Studies Depression scale (CES-D); This is a 20-item measure that asks about the frequency of depressive symptoms (affective, psychological, and somatic) within the past week.
- Overall Perceived Psychological Stress: the 10-item Perceived Stress Scale (PSS) measures overall appraisals of stress in the past month.

Analysis: Our hypotheses will be tested by analyzing the change scores (subtracting the baseline scores from the value obtained at 3 months) for the outcome measures (RMBPC, CES-D, and PSS), and comparing the results of CRA with the control condition in order to determine the efficacy of the intervention. We will determine if subjects in CRA had a significant decrease in level of burden, reduced depression, and decreased stress, when compared to the control group. We'll use univariate ANOVA (analysis of variance) to determine the level of significance for these measures.

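### The Overview randomises before baseline data and Procedures randomises after; nothing says which order governs or when the allocation is disclosed

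*Combined protocol and SAP*

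**What the plan says.** The Protocol Overview is a numbered list of five steps. After recruitment, step 2 reads "Randomize subjects: participants will be assigned to the study group or the control group". Step 3 is baseline: "Before intervention, we will collect pre-data to establish the baseline status of participants". Step 4 is delivery ("For both study and control groups, we will send instructions and materials") and step 5 is follow-up ("We will collect post-treatment data after 3 months").

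The Procedures paragraph gives a different sequence. After consent, it says "After initial assessment, subjects will be randomized to either CRA or the control condition, instructions will be distributed", and a post-intervention interview follows at 3 months.

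Methods adds only that "Outcome measures of both groups will be recorded at baseline and after 3 months", which does not place baseline before or after randomisation. The Analysis paragraph of the SAP tests the hypotheses by "analyzing the change scores (subtracting the baseline scores from the value obtained at 3 months) for the outcome measures", using univariate ANOVA, and states no adjustment for baseline. Allocation concealment and blinding are not mentioned anywhere.

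**The concern.** All three outcomes (RMBPC, CES-D and PSS) rest on the caregiver's own report of bother, depressive symptoms or perceived stress. A caregiver who already knows the assigned arm may answer the baseline questions differently from one who does not. Because baseline is subtracted from every outcome, any part of such a shift that is present at baseline and gone by 3 months goes straight into the estimated treatment effect. A part that is still present at 3 months cancels.

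There is a second route. A participant lost between Overview steps 2 and 3 would be randomised but have no baseline, and so no change score. If such losses differ by arm, the groups compared are no longer the groups randomised.

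Both problems disappear if baseline is completed before the allocation is known. The plan gives two orders and no rule on release, so a reader cannot tell whether that protection is in place.

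**Working it through.** **The two sequences side by side**

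| Position | Overview | Procedures |
|---|---|---|
| 1 | Recruit | Consent |
| 2 | Randomise | Initial assessment |
| 3 | Collect pre-data | Randomise |
| 4 | Send instructions and materials | Distribute instructions |
| 5 | Collect post-data at 3 months | Interview at 3 months |

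Positions 2 and 3 are reversed. Only Procedures puts the order into words; in the Overview it comes from the numbering. The rest of the Overview list does run in time order, and nothing marks it as non-chronological. The initial assessment in Procedures is best read as baseline, because it is paired with the post-intervention assessment and no separate screening assessment is described. If it did mean screening, no section would place baseline before randomisation.

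The two versions agree on one point: baseline comes before materials are sent. The open question is therefore knowledge of the allocation, not exposure to the intervention.

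**Illustration of what could follow**

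The plan has no figure of its own to reproduce here, and the size of any shift cannot be derived from it.

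Inputs:
- From Methods: 75 per arm, hence df = 75 + 75 − 2 = 148.
- Assumed: no true effect; two-sided alpha 0.05; equal SDs at the two times; baseline to 3-month correlation r = 0.5 (range 0.3 to 0.7); arm-related baseline shift b = 0.1, 0.2 or 0.3 SD; share p of that shift still present at 3 months = 0, 0.5 or 1.

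Formulas:
- Absolute bias in the between-arm difference in change = b(1 − p).
- Standard error of that difference, in SD units = √(2(1 − r)) × √(2/75). At r = 0.5 this is 1 × 0.163 = 0.163; at r = 0.3 it is 0.193; at r = 0.7 it is 0.126.
- A two-group ANOVA is equivalent to the two-sample t-test, so the rejection rate comes from the noncentral t with 148 df and noncentrality b(1 − p)/SE. Example: b = 0.2, p = 0, r = 0.5 gives 0.2/0.163 = 1.22 and a rejection rate of 0.229.

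False-positive rate:

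| Share persisting | r | b = 0.1 | b = 0.2 | b = 0.3 |
|---|---|---|---|---|
| None | 0.3 | 0.081 | 0.177 | 0.338 |
| None | 0.5 | 0.093 | 0.229 | 0.447 |
| None | 0.7 | 0.123 | 0.349 | 0.654 |
| Half | 0.3 | 0.058 | 0.081 | 0.120 |
| Half | 0.5 | 0.061 | 0.093 | 0.150 |
| Half | 0.7 | 0.068 | 0.123 | 0.218 |
| All | any | 0.050 | 0.050 | 0.050 |

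A simulation at r = 0.5 (40,000 runs per cell) agrees: 0.096, 0.230 and 0.446 with none persisting; 0.062, 0.093 and 0.151 with half; 0.051, 0.052 and 0.049 with all.

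**The case against.** The best case on the other side is that this is a loose outline set against an operational section. Procedures gives the conventional order in words, while step 3 of the Overview is anchored only to the start of the intervention, which is true under either order. In both versions the first contact with participants described after randomisation is the sending of instructions or materials, after baseline, and nothing suggests that they are told their arm sooner. Harm needs a chain of events: the outline is followed instead of Procedures, the allocation is disclosed early, disclosure shifts the answers by arm, and the shift fades by 3 months. Every input to the illustration except the arm size is assumed.

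Much of this stands. The plan does not show that baseline was to be taken with the allocation known. The larger percentages need the largest assumed shift with no persistence. Some persistence is plausible, because one arm receives an app ("Participants will receive the Caring Response mobile app containing the coping skills training") and the other a workbook with online resources, so participants probably know by 3 months what they were given. The figures should not be read as evidence about this trial. It is also fair that silence on disclosure would be a gap even if the two sections agreed.

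It does not remove the point. Staff working from the numbered list would randomise first, no sentence tells them to follow Procedures instead, and no sentence tells them to hold the allocation back.

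**Conclusion.** The concern holds. The two sections state opposite orders for randomisation and baseline, and the plan neither settles which governs nor says when the allocation is released. This is certain from the text. The consequence is conditional: it arises only if the Overview order is followed and the allocation is known before baseline is complete. The documents give no basis for the size or direction of any resulting shift.

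Under the assumptions listed, with r = 0.5, the false-positive rate would be about 9%, 23% or 45% for shifts of 0.1, 0.2 or 0.3 SD if none persists, about 6%, 9% or 15% if half persists, and 5% if all persists or there is no shift. Over r = 0.3 to 0.7 the ranges are 8–12%, 18–35% and 34–65% (none persists) and 6–7%, 8–12% and 12–22% (half persists).

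It should be fixed because the baseline enters every change score and the correction is almost free. Reporting that differs by arm at 3 months is possible under either order and is a separate matter.

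**What to change.** Reorder the Overview to match Procedures:

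1. Recruit and obtain consent.
2. Confirm eligibility and complete all baseline RMBPC, CES-D and PSS measures.
3. Randomise.
4. Deploy the treatments.
5. Collect post-data.

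Add one sentence stating that a participant's allocation is generated or released only after that participant's baseline record is complete. If enrolment has already begun, state the order actually used.

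The cost is two swapped steps, one added sentence, and the short mentions of consent and eligibility in steps 1 and 2. Sample size, measures and analysis do not change. The fix removes the baseline part of the problem; it does not address reporting by arm at 3 months.

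### The three main outcomes are compared by change-score ANOVA with no baseline covariate; ANCOVA on the same data would be more precise and would remove the effect of chance imbalance in the baseline score.

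*Combined protocol and SAP*

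**What the plan says.** The Analysis paragraph of the SAP tests the hypotheses by "analyzing the change scores (subtracting the baseline scores from the value obtained at 3 months") for RMBPC, CES-D and PSS. It then compares the arms and will "use univariate ANOVA (analysis of variance) to determine the level of significance for these measures". No covariate, adjusted model or sensitivity analysis is named anywhere. The plan does not use the word unadjusted, but that is the plain reading of a univariate ANOVA on change scores.

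The covariate already exists. Under Methods, "Outcome measures of both groups will be recorded at baseline and after 3 months". Under Procedures, "After initial assessment, subjects will be randomized to either CRA or the control condition", and no stratification or balancing on baseline scores is described. Enrolment is fixed at 150, with 75 per arm, and no power calculation is given.

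**The concern.** Subtracting baseline is the same as adjusting for it with a slope of exactly 1. For self-report scales taken 3 months apart, with similar spread at both visits, the slope is expected to be below 1, so the change score over-corrects. There are two consequences.

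- **Precision.** The change score carries baseline noise that a fitted slope would remove. This lowers power on all three main outcomes in a sample that is already fixed and has no stated margin.
- **Chance imbalance.** If one arm starts worse on a scale, regression to the mean makes it appear to improve more, and the change-score difference counts this as treatment effect. A positive result with a worse-starting CRA arm, or a null result with a worse-starting control arm, would be open to that challenge.

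**Working it through.** **Inputs from the documents.** 75 participants per arm; each outcome measured at baseline and 3 months; analysis variable is 3-month value minus baseline; no covariate. The plan's 150 cannot be reproduced, because no alpha, power, effect size or SD is given.

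**Assumptions.** Two-sided alpha 0.05; SD of each score s, equal at the two visits; baseline-to-3-month correlation r, shown from 0.3 to 0.9; all 75 per arm assessed.

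**Step 1: variance.** Per participant, the change score has variance 2(1−r)s² and the ANCOVA residual has variance (1−r²)s². The ratio is (1−r²)/[2(1−r)] = (1+r)/2. The equivalent total sample is 150 ÷ [(1+r)/2]. Detectable differences use (1.96 + 0.84) × √(2/75) × the relevant SD.

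| r | Variance ratio | Equivalent N | Detectable difference at 80% power, change (SD) | Same, ANCOVA (SD) |
|---|---|---|---|---|
| 0.3 | 0.65 | 231 | 0.541 | 0.436 |
| 0.4 | 0.70 | 214 | 0.501 | 0.419 |
| 0.5 | 0.75 | 200 | 0.457 | 0.396 |
| 0.6 | 0.80 | 188 | 0.409 | 0.366 |
| 0.7 | 0.85 | 176 | 0.354 | 0.327 |
| 0.9 | 0.95 | 158 | 0.205 | 0.199 |

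**Step 2: power for a true effect of 0.40 SD** (noncentral t, 75 per arm).

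| r | Change-score ANOVA | ANCOVA |
|---|---|---|
| 0.5 | 0.682 | 0.802 |
| 0.6 | 0.777 | 0.860 |
| 0.7 | 0.881 | 0.926 |
| 0.8 | 0.970 | 0.982 |

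A simulation of 10,000 trials at r = 0.5 gave 68.3% and 79.9%, which agrees.

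**Step 3: chance imbalance.** The standard error of the baseline difference is √(2/75) = 0.163 SD. Given a baseline difference D, the change-score estimate is shifted by (1−r)D in favour of the worse-starting arm. At r = 0.5:

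| Imbalance | D (SD) | Shift (SD) | Type I error given that imbalance |
|---|---|---|---|
| none | 0 | 0 | 0.024 |
| 1 SE | 0.163 | 0.082 | 0.048 |
| 1.5 SE | 0.245 | 0.122 | 0.082 |
| 2 SE | 0.327 | 0.163 | 0.134 |

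At 2 SE the conditional type I error is 0.117 for r = 0.6 and 0.101 for r = 0.7. An imbalance of 2 SE or more, in either direction, arises in about 4.6% of trials per outcome.

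In the simulation at r = 0.5 with a true effect of −0.40, both methods averaged −0.40 over all trials. In the trials where the CRA arm started clearly higher (mean imbalance 0.25 SD), the change-score mean was −0.53 and the ANCOVA mean −0.40.

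**Step 4: CES-D.** High depressive symptoms are an exclusion criterion, so the baseline is cut off at the top. Over-correction adds (1−r)² × Var(baseline) to the residual variance, and truncation shrinks Var(baseline). At r = 0.5 (r and SD being those before truncation):

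- Cut at +1 SD: Var(baseline) = 0.630, ratio 0.75/(0.75 + 0.25 × 0.630) = 0.83.
- Cut at 0 SD: Var(baseline) = 0.363, ratio 0.75/(0.75 + 0.25 × 0.363) = 0.89.

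The gain is smaller but remains. With the cut at +1 SD, simulated power was 73.4% for change scores and 80.4% for ANCOVA.

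**The case against.** The strongest reply is that the planned test is valid. Under randomisation, change-score ANOVA is unbiased over repeated allocations and keeps its type I error at 0.05. That stands, and the conditional figures must be read with it: the 13% belongs to a 2 SE imbalance, which is uncommon. At 1 SE there is no inflation, and with no imbalance the test is conservative. The average absolute shift is about 0.065 SD at r = 0.5 and 0.039 SD at r = 0.7.

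The size of the gain is also unknown from the documents. If the scales are very stable the saving is slight, and if the SDs at the two visits differ the slope could lie nearer 1. That stands too, but it does not reverse the comparison. The change-score variance exceeds the ANCOVA residual variance by (1−slope)² × Var(baseline), which is never negative; ANCOVA pays one degree of freedom.

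ANCOVA on one baseline score removes the linear effect of imbalance in that score only, not in other characteristics. This is correct and limits the claim.

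Finally, the protocol Overview lists randomisation as step 2 and baseline data as step 3, whereas Procedures puts the assessment first. The order should be confirmed. The planned change score uses the same baseline, so the ambiguity gives no reason to prefer it.

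**Conclusion.** The concern holds. The plan collects the covariate it needs and then uses it in a less efficient way on all three main outcomes. With equal SDs, ANCOVA removes 15% to 30% of the variance for r between 0.7 and 0.4, and 5% at r = 0.9. At r = 0.5 the planned analysis discards the equivalent of about 50 participants (200 − 150). ANCOVA also removes the shift of (1−r) times any chance imbalance in the outcome's own baseline. These sizes depend on the assumed r, SDs, alpha and complete follow-up. The direction holds whenever the slope differs from 1. This is an improvement that should be made; it does not make the planned test invalid.

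**What to change.** Replace the ANOVA sentence in the Analysis paragraph with text such as:

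> For each outcome (RMBPC, CES-D, PSS) the primary analysis will be an ANCOVA of the 3-month score, with treatment arm as factor and the baseline value of that outcome as covariate. The adjusted mean difference with its 95% confidence interval is the effect estimate.

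The change score may stay as the dependent variable if the sponsor prefers that wording: with baseline in the model the treatment estimate is identical. The ANOVA without a covariate can be kept, labelled as a sensitivity analysis. The SAP should also state that baseline is measured before allocation, and the change should be fixed before outcome data by arm are seen.

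The cost is one sentence and one degree of freedom per outcome, with no new data, visits or participants.
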